4.2. Per Protocol Analysis Set

The Per Protocol Analysis Set (PPAS) will be a subset of the FAS dataset. The primary analysis of the efficacy endpoints will be based on the FAS, with a sensitivity analysis conducted on the PPAS, which will include all subjects who were not major protocol deviators. Each deviation will be reviewed on a case by case basis to determine whether the subject should be excluded from the PPAS (based on Table 3).

Table 3 Potential reasons for exclusion of a subject from the PPAs

Exclusion of a subject	Responsibility	Action/Source	Required Listings from Programming
No valid primary efficacy measurement post-baseline (i.e. no readings in 24h UPCR at Weeks 5, 9 or 13)	Programmer/ Clinical/ Statistician	
Programming check to highlight any subject with incomplete data, and those subjects with no primary efficacy readings at the scheduled time point.
 
Listing will be reviewed by the clinician and statistician to determine if there is insufficient data.
	Listing of whether primary efficacy reading was completed (including date/times of measurements).
Change in background treatment for FSGS (e.g. starting new immunosuppressant or increasing the dose of background steroids)	Programmer/ Clinical/ Statistician	Listing will be reviewed by the clinician and statistician to determine if subjects' change in background immunosuppressant medication (i.e. change of dosage or frequency) could have impact on efficacy	Listing of immunosuppressant medication (including dosage and frequency throughout study)
Falsely enrolled into study despite violating inclusion/exclusion criteria	Programmer/ Clinical/ Statistician	Review of all screening and baseline data listings.	Screening/Baseline data listings
Outside the visit window (± 3 days) for the final primary endpoint time point (Week 13)	Programmer/ Clinical/ Statistician	Review of actual study day (collection date – first dosing date +1) for Week 13 visit. The window is 80~87.	Listing of actual study day for all subjects at Week 13.
Did not receive all specified doses of PF-06730512 as per protocol (i.e. missed dose not due to withdrawal from study)	Programmer/ Clinical/ Statistician	Programming check to highlight any subject who missed 1 or more dose of PF-06730512	Listing of study medication.

4.3. Safety Analysis Set

The Safety Analysis Set (SAS) is defined as all enrolled subjects who have received at least one dose of study treatment.

4.4. Other Analysis Sets

4.4.1. PK Concentration Analysis Set

The PK Concentration Analysis Set is defined as all enrolled subjects treated who received at least one dose of PF-06730512 and have at least 1 measurable concentration.

Subjects who experience events that may affect their PK profile (e.g. dosing error) may be excluded from the PK analysis. At the discretion of the pharmacokineticist a concentration value may also be excluded from PK summaries if the deviation in sampling time is of sufficient concern or if the concentration is anomalous for any other reason.

4.4.2. PK Parameter Analysis Set

The PK parameter analysis population is defined as all enrolled subjects treated who have at least 1 of the PK parameters.

4.4.3. Immunogenicity Analysis Set

The immunogenicity analysis population includes all treated subjects with at least 1 ADA sample (pre-dose or post-treatment) analyzed. If a subject only has pre-dose baseline data and no post-treatment immunogenicity data, this subject is not evaluable for subject-level ADA and NAb status and should not be included in subject-level data analysis (eg. overall ADA/NAb incidence, duration of ADA/NAb response).

5. GENERAL METHODOLOGY AND CONVENTIONS

The planned statistical methods and analyses for the primary and secondary endpoints are described in detail in Sections 6.1 and 6.2 below **CCI**

5.1. General Format

All tables, figures and listings for the final analyses will include titles/footnotes indicating the file in which the item is located and the date on which the item was produced as per Pfizer standards. All tables, figures and listings will also have a subtitle that will indicate the population on which the presentation is based.

5.2. Hypotheses and Decision Rules

No classical hypothesis testing will be done, as decisions will be based on Bayesian (posterior) probabilities. This Bayesian interpretation is based on the assumption that the model provides an adequate approximation to a Bayesian analysis with “vague” priors for all parameters in the model.

For final analysis, the decision criteria are given below and apply to each dose of PF-06730512 separately:

- *C1: At least 95% confident that the PF-06730512 reduction > 0%;*

- *C2: At least 50% confident that the PF-06730512 reduction > 35%.*

Interim Bayesian decisions, that is, the posterior predictive probability that at an interim analysis where less than the entirety of the cohort has been enrolled, that decisions C1 and C2 would be achieved once full enrollment has completed were performed at IA1 and IA3 for cohorts 1 and 3, respectively. Those probabilities will not be reproduced here. For the CSR, Table 14.2.1.1.7 and Table 14.2.1.1.6, Summary of Predictive Probabilities based on 24-Hour Urine Collection, at IA1 and IA3 using IA1 FAS and IA3 FAS may be used to present interim findings in the CSR.

5.3. General Methods

5.3.1. Summary Analyses for Continuous Data

Continuous variables will be presented using summary statistics: number of observations, arithmetic mean, standard deviation, median, minimum and maximum values. For endpoints to be analysed on the natural log scale, the geometric mean and geometric coefficient of variation will additionally be calculated.

5.3.2. Summary Analyses for Categorical Data

Categorical variables will be presented using summary statistics: number of observations, counts and percentages in each category.

5.3.3. Mixed Model Repeated Measures (MMRM)

The efficacy analyses over time will be based on the FAS and will use a mixed model repeated measures (MMRM) approach. The mixed effect repeated measures model will include baseline, week (as a factor), baseline*week interaction, and will use an unstructured covariance matrix for within-subject time-dependent correlation.

If convergence is not obtained or model fit is not adequate then other covariance structures will be investigated as necessary. The Kenward-Roger approximation will be used for estimating degrees of freedom for the model parameters.

The probabilities for the decision criteria (listed in Section 5.2) for each of the doses (as required) will be calculated using the results of the MMRM (e.g. back-transformed LSmean estimate, standard error and degrees of freedom for Week 13).

[figure not shown]
[figure not shown]
[figure not shown]
The Least Squares Means (LSMeans) (back-transformed if log_e transformation is performed) together with 90% confidence intervals and standard errors will be obtained for each dose individually (if applicable) and week, and will be summarized in a table and a profile plot with a separate plot for each dose (if applicable).

Ratios in LSMeans (calculated by back-transforming modelled results if \log_e transformation is performed), between doses at the different weeks, together with 90% confidence intervals and standard errors, will also be obtained if applicable.

CCI

CCI

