1. VERSION HISTORY

This CSR Statistical Analysis Plan (SAP) for study **C0221002** is based on **Protocol Amendment 5** dated **18-Aug-2021**.

Table 1. Summary of Changes

Version/ Date	Associated Protocol Amendment	Rationale	Specific Changes
2 08 FEB 2023	5 18 Aug 2021	Updates to minor components of analysis due to recent FDA guidance, CCI	
 • CCI [REDACTED] • further clarification on analysis and presentation of multiple dose levels; • inclusion of robust standard error estimation included in SAS code due to updated FDA guidance on controlling for covariates in randomized controlled trials; • update sample SAS code due to incorrect coding in previous version; • update to language on missing values being imputed by MMRM; • CCI [REDACTED]
2 08 FEB 2023	5 18 Aug 2021	Changes needed based on Protocol Amendment 5	
 • Updated study objectives, study design and statistical methods to extend treatment duration from 12 weeks to 24 weeks, and to add an optional cohort (Cohort 3) to potentially explore a higher dose of PF-06730512 CCI [REDACTED] in subjects with FSGS, based on emerging data from the study.
2 08 FEB 2023	4 12 Jun 2020	Changes needed based on emerging data to incorporate into IA1 and align with current IA Charter	
 • Included PPAS analysis into IA readouts due to emerging discontinuations in the study (Section 4.2, 6.1.1.2 and Appendix 1.1). • Added predictive probability table related to first morning void sensitivity analysis as was required based on IA Charter (version 1.0) (Section 6.1.1.2 and Appendix 1.1). • Added safety summaries that may be required at IA2 and/or IA3 due to potential need for internal business decision making or external briefing documents (Section 6.5). • Clarified definition of baseline UPCR in case of scenario where Week -1 values were missing (Section 3.1.1).

			
• CCI [REDACTED]• Updated study objectives and study design to align with current protocol (Section 2.1.3 and 2.2) and removed any mention of “Part B”.• Clarified minor points for individual profile plots (Section 6.1.1.1).• Updated demographic tables as required for IA readouts (Sections 6.4.2 and 6.4.3).• Note: Minor formatting issues were identified during QC performed after 22 Dec 2020 final draft version and were the only edits incorporated after database snapshot for IA1.• Included clinical output assessments, PK, ADA/Nab.

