3. ENDPOINTS AND BASELINE VARIABLES: DEFINITIONS AND CONVENTIONS

3.1. Primary Endpoint(s)

CCI

3.1.1. Percentage change from baseline to Week 13 in Urinary Protein to Creatinine Ratio (UPCR) based on 24-hour urine collection

The primary efficacy endpoint is the percentage change from baseline to Week 13 in the Urinary Protein to Creatinine Ratio (UPCR) based on 24-hour urine collections. UPCR will be calculated as urinary protein divided by the urinary creatinine value at the same collection time point. If a value of protein or creatinine is missing, UPCR will be missing for that respective value.

Baseline for the primary endpoint is defined as the Week -1 UPCR measurement that is based on the 24-hour urine collection. If the Week -1 24-hour UPCR value is not available, the nearest 24-hour UPCR measurement taken to the Week -1 visit will be used, provided it is pre-dose.

For sensitivity analyses utilizing first morning void UPCR assessments instead, the baseline is similarly defined as the Week -1 first morning void UPCR measurement. If the Week -1 first morning void UPCR value is not available, the nearest first morning void UPCR measurement taken to the Week -1 visit will be used, provided it is pre-dose.

Log-transformed change from baseline (i.e. the difference in \log_e -transformed values) will be the dependent variable in the analysis models. The results from the analysis models will be back-transformed to obtain the ratio to baseline. The percentage change from baseline will be derived by transforming the ratio using the following formula:

$$\text{Percentage change from baseline} = 100 * ([\text{back-transformed LSMean}] - 1)$$

For descriptive summaries, percentage change from baseline will be calculated as the Week 13 measurement minus the baseline value divided by the baseline value multiplied by 100.

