6.1.1.1. Primary Analysis

The primary analysis will be based on the FAS. A MMRM approach as specified in Section 5.3.3 will be fit to the post-dose 24-hour urine collection data on UPCR (i.e. Weeks 5, 9 and 13). All UPCR values (including baseline) will be \log_e -transformed prior to analyses. The primary analysis will include the change from baseline values of UPCR (on the \log_e -scale) as the dependent variable.

Absolute values and percentage changes from baseline in UPCR (based on 24-hour urine collection) will be summarized descriptively by dose (if applicable) and timepoint as described in Section 5.3.3. Tables will present all Lead-in Period, baseline and post-baseline time points where applicable. All 24-hour urine collection data will be included in the data listings.

The probabilities for the decision criteria for each of the doses (as required) will be calculated directly from the results of the MMRM. These are the probabilities that the reduction from baseline due to PF-06730512 (each dose level) is greater than (i) 0% and (ii) 35%. The LSMeans at Week 13 will be used to derive the posterior probabilities associated with the decision criteria.

A table showing the estimate of the mean of the posterior distribution for the percentage change from baseline for each dose of PF-06730512 (if applicable), the 90% credible interval and the posterior probabilities of passing the decision criteria will be produced (Appendix 3).

The following results from the above primary analysis will be plotted:

- Individual profile plots of the raw values (including all time points from Week -8, to Week 33) against time. Two plots per dose will be generated of absolute values and percentage changes from baseline. To distinguish between subjects enrolled before and after amendment 5, assessments from each individual's Follow-up Period will be interpolated with a different line style (e.g., a dashed line) than assessments from the Investigational Treatment Period.
- Profile plots of the back-transformed LSMeans (including 90% confidence intervals) over time, with a separate line included for each dose (if applicable).

No imputation of missing values will be conducted and all available data through Week 13 will be used in the MMRM models.

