6.1.1.2. Sensitivity/Robustness Analyses

The following sensitivity analyses to the primary endpoint will be carried out:

- CCI
[REDACTED]
- The primary efficacy endpoint will be analyzed for individual dose levels separately, and will follow the format described in section 5.3.3 and 5.3.4..
- The primary efficacy endpoint of % change from baseline in UPCR at week 13, and for all study weeks will be performed including the following potentially relevant covariates: GFR; disease duration (quantized into four categories);; and FSGS type, as measured by Columbia Classification consisting of the following categories: PERIHILAR, CELLULAR, COLLAPSING, NOT OTHERWISE SPECIFIED. In the event the model does not converge due to sparseness in FSGS type, for example, a modified model excluding sparse covariates that impact model performance will be performed.
- CCI
[REDACTED]
- CCI
[REDACTED]
- The primary analysis MMRM model described in Section 6.1.1.1 will be repeated using the associated PPAS.

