Appendix 2. STATISTICAL METHODOLOGY DETAILS

Appendix 2.1. Example SAS code for Statistical Analyses

Primary Analysis [Mixed Model Repeated Measures (MMRM)]:

Note: Loge_endpoint = log(UPCR at week x) – log(baseline)

CCI

[figure not shown]
CCI

CCI

[figure not shown]

CCI

CCI

- CCI
- 

- CCI
- 
- 

CCI

CCI
CCI
CCI

A large, bold, red watermark with the letters 'CCI' is centered on the page. The 'C' is a circle with a vertical line through it, and the 'I' is a vertical line with a horizontal bar at the top. The entire watermark is set against a black rectangular background.

CCI

CCI

A series of horizontal black redaction bars of varying lengths, with the first two containing the text 'CCI' in red. The redaction bars are positioned in a descending staircase pattern from top-left to bottom-right.

CCI

CCI

[figure not shown]
CCI

CCI

[figure not shown]

[figure not shown]
		CCI			
...					

CCI

CCI

CATEGORICAL CLASSES FOR ECG AND VITAL SIGNS OF POTENTIAL CLINICAL CONCERN

Categories for QTcF

QTcF (ms)	450< max. \leq 480	480< max. \leq 500	max. $>$ 500
QTcF (ms) increase from baseline	30< max. \leq 60	max. $>$ 60	

Categories for PR and QRS

PR (ms)	max. \geq 300
PR (ms) increase	Baseline $>$ 200 and Baseline \leq 200 and

from baseline	and max. $\geq 25\%$ increase	max. $\geq 50\%$ increase
QRS (ms)	max. ≥ 140	
QRS (ms) increase from baseline	$\geq 50\%$ increase	

Categories for Vital Signs

Systolic BP (mm Hg)	min. < 90	
Systolic BP (mm Hg) change from baseline	max. decrease ≥ 30	max. increase ≥ 30
Diastolic BP (mm Hg)	min. < 50	
Diastolic BP (mm Hg) change from baseline	max. decrease ≥ 20	max. increase ≥ 20
Supine pulse rate (bpm)	min. < 40	max. > 120

Measurements that fulfill these criteria are to be listed in the report.

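### Are the C1 and C2 posterior probabilities put on the wrong scale because SAP 5.3.3 names a back-transformed LSMean as an example input?

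*SAP*

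**What the plan says.** SAP 5.2 replaces hypothesis testing with two posterior criteria applied to each dose: C1, at least 95% confident that the reduction exceeds 0%, and C2, at least 50% confident that it exceeds 35%. The posterior is read from the fitted model, treated as approximating a Bayesian analysis with vague priors.

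The response is on the log scale. The note above the code in SAP Appendix 2.1 defines it starting "Loge_endpoint = log(UPCR at week x" and then subtracts log baseline. SAP 3.1.1 adds: "The results from the analysis models will be back-transformed to obtain the ratio to baseline".

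The inputs to the probabilities are described in two places:

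- SAP 5.3.3 mentions, after an e.g., the "back-transformed LSmean estimate, standard error and degrees of freedom for Week 13". It also says: "The Kenward-Roger approximation will be used for estimating degrees of freedom for the model parameters".
- SAP 6.1.1.1 says the probabilities are calculated directly from the MMRM results, and that "The LSMeans at Week 13 will be used to derive the posterior probabilities associated with the decision criteria". It then plans a table with the "estimate of the mean of the posterior distribution for the percentage change from baseline for each dose of PF-06730512", a 90% credible interval and the probabilities.

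SAP Table 1 (version history) records the "inclusion of robust standard error estimation included in SAS code due to updated FDA guidance on controlling for covariates in randomized controlled trials". SAP 6.1.1.2 plans a sensitivity analysis that "will be performed including the following potentially relevant covariates", naming GFR, disease duration and FSGS type.

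**The concern.** If the model is normal on the log scale, the t posterior is that of the mean log ratio. Putting a back-transformed LSMean into a t calculation gives a different posterior, and the direction of the error depends on the scale of the standard error, which SAP 5.3.3 does not state. Two programmers reading that sentence literally could report different values for C1, the only criterion that asks whether there is any effect, in a study with no classical test beside it.

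Two further points add to the doubt. The mean of an exponentiated t variable is not finite, so a posterior mean for percentage change does not strictly exist; the back-transformed LSMean is the posterior median. And robust standard errors, introduced by reference to guidance for randomized trials, appear beside Kenward-Roger degrees of freedom in a non-randomized study with small cohorts. An uncorrected sandwich estimate tends to be too small at such sizes.

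**Working it through.** The legible text contains no SD, power figure or worked probability, so there is no figure of the plan's own to reproduce.

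**Inputs.** Thresholds of 0% and 35% and confidence levels of 95% and 50% (SAP 5.2). About 18 subjects at the full Cohort 1 analysis (Protocol 9.6) and up to about 22 per cohort (Protocol Summary). Assumptions: log SD of 0.4 to 0.7; SE = SD/√n; n − 2 degrees of freedom in place of Kenward-Roger.

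**Three readings.** R is the observed ratio to baseline, SE is on the log scale, and c is 1 for C1 or 0.65 for C2.

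- Log scale (correct): P = T[(ln c − ln R)/SE]
- Ratio with delta-method SE: P = T[(c − R)/(R × SE)]
- Ratio with log-scale SE (mixed): P = T[(c − R)/SE]

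For any R below 1, 1 − R < −ln R < (1 − R)/R. The mixed form therefore always understates C1 and the delta form always overstates it.

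**Cut-offs at n = 18, SD 0.55.** SE = 0.55/√18 = 0.130 and t(16) = 1.746, so t × SE = 0.226. C1 passes when R is below:

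- log: exp(−0.226) = 0.797
- delta: 1/(1 + 0.226) = 0.815
- mixed: 1 − 0.226 = 0.774

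**Probabilities at an observed R of 0.80, same setting.**

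| Reading | P(reduction > 0%) | P(reduction > 35%) |
|---|---|---|
| Log | 0.948 | 0.064 |
| Delta | 0.964 | 0.084 |
| Mixed | 0.929 | 0.132 |

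C1 passes on the delta reading alone. C2 fails on all three.

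**C1 pass rate with no true effect** (400,000 simulated trials per setting, n = 18, SD 0.4 / 0.55 / 0.7):

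- log: 5.0 / 5.0 / 5.0%
- delta: 6.1 / 6.6 / 7.1%
- mixed: 3.8 / 3.4 / 3.0%

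At n = 22 the delta range is 6.1–7.0% and the mixed range 3.2–3.9%. With a true ratio of 0.80 (n = 18, SD 0.55), C1 passes 50% (log), 57% (delta) or 42% (mixed) of the time.

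**C2.** At R = 0.65 every numerator is zero, so every form gives exactly 0.50. The rule reduces to whether R is below 0.65, whatever the scale.

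**Both criteria together.** At R = 0.65, C1 is the binding criterion only when t × SE exceeds −ln 0.65 = 0.431. At n = 18 that needs SD > 0.431 × √18/1.746 = 1.05; at n = 22 (t = 1.725), SD > 1.17. For the mixed form 0.35 replaces 0.431, giving 0.85 and 0.95. All of these lie above the assumed range. In simulation at true ratios of 1.0, 0.80 and 0.65, the joint pass rate under the delta form agrees with the log scale to within 0.1 points. The largest mixed-form shift is from 50.0% to 49.1% (n = 18, SD 0.7, ratio 0.65).

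**The case for a change.** The strongest case for a change is that SAP 5.3.3 is the fuller description of the inputs, that it puts the wrong kind of estimate beside a standard error and degrees of freedom, and that the resulting probabilities are the primary reported result. If the hidden code is right, the prose describes it badly; a few sentences would cure that at no cost to design or data.

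The arithmetic behind this stands: at an observed ratio of 0.80 the reported C1 probability ranges from 0.929 to 0.964, on either side of the 95% bar. With a larger SD more could move. At n = 18, SD 1.0 and an observed 35% reduction, C1 is 0.957 on the log scale and 0.922 in the mixed form.

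The step from there to a defect does not stand. Neither wrong calculation is prescribed; each is a guess at how an illustrative parenthesis might be programmed. SAP 6.1.1.1, which is specific to the primary analysis, points to the direct output of a log-scale model, and a reduction above 35% is the same event as a log ratio below ln 0.65. The Appendix 2 code and the Appendix 3 material cited for the results table cannot be read, so a formula missing from view is not known to be missing from the plan.

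The robust-error point is weaker still. It rests on one line of a change table that names no model. Its stated reason, covariate control, fits the covariate-adjusted sensitivity analysis at least as well as the primary model, and nothing says that the estimator is uncorrected.

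**Conclusion.** No change to the plan is needed. SAP 5.3.3 is loosely worded about the scale of the standard error, but the plan can be followed as written to the correct log-scale posterior, and that is how an analyst holding the LSMean, standard error and degrees of freedom from a log-scale model would naturally proceed. Calling the back-transformed estimate a median would alter no number, because SAP 3.1.1 already fixes the reported percentage change as 100 × (back-transformed LSMean − 1).

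The most a misreading could do, at n = 18 and an assumed log SD of 0.4 to 0.7, is shift the no-effect C1 pass rate from 5.0% to between 3.0% and 7.1%. C2 pass or fail never changes, and the joint result moves by at most about 0.9 points, because C2 is the harder criterion at these SDs. That would weaken only if the log SD were above about 0.85 at n = 18 and the mixed calculation had actually been programmed; nothing legible indicates the latter. For an open-label, non-pivotal Phase 2 study, this is missing detail with almost no bearing on the conclusion.
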